### Protocol Change History

Version	Description	Changed By
1.0	New	
1.1	Removed Flexion / extension x-rays at 6 months. Noted that 24 month CT may be collected for patients that did not demonstrate fusion at 12 months. Updated date and version number.	

CONFIDENTIAL

This material is the property of Stryker Spine. Do not disclose or use except as authorized in writing by Stryker.  
Page 2

## Study Synopsis

Title	A Prospective Multi-Center Evaluation of a hydraulic expandable TLIF cage for the treatment of Degenerative Disc Disease of the Lumbar Spine
Short Title	APROPOS (AccuLIF® Prospective Patient Outcomes Study)
Protocol Number	2015-L-001
Phase	Post-Market
Methodology	This is a prospective, post-market, multi-center, clinical evaluation of the AccuLIF expandable TLIF cage in patients requiring arthrodesis for degenerative disc disease (DDD) or DDD with up to Grade I spondylolisthesis or retrolisthesis at one or two contiguous levels between L2 and S1. DDD is defined as back pain of discogenic origin with degeneration of the disc confirmed by history and radiographic studies.
Study Duration	Enrollment period: approximately 9 months Study follow-up period: each subject will be followed for 24 months (2 years) Total study duration: approximately 36 months
Study Center(s)	Up to 10 centers in the US will participate
Hypothesis	
It is hypothesized that patients implanted with the AccuLIF expandable TLIF cage will show restoration of anterior, middle, and posterior disc height, improve segmental lordosis and maintain regional and global sagittal balance post operatively.
 
Primary success is defined as an increase of 3 degrees or more of segmental lordosis post operatively.
 
It is also hypothesized that patients implanted with the AccuLIF expandable TLIF cage will show improvement in post-operative clinical outcomes when compared to pre-operative clinical status.

CONFIDENTIAL

This material is the property of Stryker Spine. Do not disclose or use except as authorized in writing by Stryker.  
Page 7


Objectives
	
Primary:
 

• To compare pre-operative and postoperative radiographic outcomes of a cohort treated for lumbar degenerative disease at one or two contiguous levels implanted with the AccuLIF expandable TLIF cage via TLIF procedure with supplemental fixation. Primary Radiographic parameters are defined as:

○ Disc height (anterior, middle, posterior in millimeters)

○ Foraminal height

○ Segmental lordosis (at each TLIF level in degrees)

○ Regional Lordosis: (inferior endplate T12-S1 in degrees)

○ Sagittal balance: (C7-S1 in millimeters)

• Primary success is defined as an increase of 3 degrees or more of segmental lordosis post operatively.

 
Secondary:
 

• To observe surgical parameters of the AccuLIF cohort. Defined as; operative time, estimated blood loss and length of stay.

• To assess the occurrence of neurologic complications by comparing pre-operative and postoperative neurologic evaluation.

• To assess clinical outcomes by comparing pre and post-operative patient measured outcomes defined as VAS, ODI and quality of life (QOL) as measured by SF-12 of the AccuLIF cohort.

• To observe the occurrence and frequency of additional complications of the AccuLIF cohort, including infection and nonunion.

• To observe standard radiographic outcomes defined as; fusion status, cage placement, migration / subsidence and parameters of supplemental fixation hardware including screw placement and subsidence.

--------------------------	--

	
Exploratory:
 

• To evaluate the percentage of subjects that achieve <math>> 3^\circ</math> lordosis and no negative changes in regional lordosis and global sagittal balance.

• To compare changes in disc height, lordosis, sagittal balance as categorized by disc morphology. Disc morphologies are defined as:

○ Tall and lordotic Average Disc Height <math>\geq 11</math> mm AND Disc Angle <math>> 12^\circ</math>.

○ Moderate Average Disc Height <math>\geq 7</math> mm to <math>\leq 10</math> mm AND Disc Angle <math>\geq 5^\circ</math> to <math>\leq 12^\circ</math>.

○ Flat and compressed: Average Disc Height 0 mm to <math>\leq 6</math> mm AND Disc Angle <math>0^\circ</math> to <math>< 5^\circ</math>.

• To compare summary AccuLIF data to published literature of comparable TLIF outcomes.

Number of Cases	Approximately 100 subjects will be enrolled in this study.

CONFIDENTIAL

This material is the property of Stryker Spine. Do not disclose or use except as authorized in writing by Stryker.  
Page 9


Diagnosis and Main Inclusion/Exclusion Criteria
	
Inclusion criteria:
 

1. Subject is skeletally mature and between 18 and 70 years of age.

2. Subject has one or more of the following diagnoses: DDD or DDD with up to Grade I spondylolisthesis or retrolisthesis, requiring decompression and arthrodesis at one or two contiguous levels between L2 and S1 as confirmed by CT, MRI, myelography and/or lateral flexion/extension films.

3. Subject has not previously undergone surgery (other than microdiscectomy / laminectomy) at the same or adjacent level.

4. Subject has received conservative (non-surgical) treatment for back pain for a minimum of 6 months and is unresponsive.

5. Subject understands the conditions of enrollment and is willing to sign and date the Informed Consent.

6. Subject agrees to comply with visit schedule and completing study questionnaires.

 
Exclusion criteria:
 

1. Subject has significant instability of the spine, e.g. isthmic spondylolisthesis or degenerative spondylolisthesis greater than grade 1.

2. Subject has degenerative disorder that requires TLIF at more than 2 levels between L2 and S1.

3. Subject has previously undergone lumbar spine surgery (other than microdiscectomy / laminectomy) at the same or adjacent level.

4. Subject is younger than 18 years of age, or older than 70 years of age.

5. Subject has a BMI of 40 or greater.

6. Subject has a history of metabolic bone disease as defined by any of the following:

a. Subject is currently taking prescription medications that increase bone-mineral density (e.g Fosamax®, Didronel®, Forteo®, Zometa®).

b. Subject was previously diagnosed with a metabolic bone disease (e.g. lumbar Paget's disease, osteoporosis or osteomalacia)

c. Subject has a history of bone fractures suggesting bone disease.

d. Subject has any other metabolic bone disease to a degree that lumbar spine instrumentation would be contraindicated.

7. Subject is osteoporotic. Subject is taking any of the following medications:

a. Chronic oral or IV corticosteroid therapy (this is not intended to exclude inhalation medication for asthma)

b. Medications known to potentially interfere with bone/soft tissue healing (e.g. methotrexate).

c. Prescription medications that increase bone-mineral density (e.g Fosamax®, Didronel®, Forteo®, Zometa®).

8. Subject has diabetes mellitus requiring daily insulin management.

---	---

CONFIDENTIAL

This material is the property of Stryker Spine. Do not disclose or use except as authorized in writing by Stryker.  
Page 10

	

9. Subject has any of the following:

a. Progressive neuromuscular disease; OR

b. Rheumatoid arthritis or other autoimmune disease; OR

c. Active malignancy within the last 15 years (unless the malignancy was treated with curative intent and there have been no clinical signs or symptoms for at least 5 years); OR

d. Active hepatitis; OR

e. AIDS, ARC, or is HIV positive; OR

f. Syringomyelia at any spinal level; OR

g. Any other condition that would interfere with the subject self-assessment of pain, function or quality of life.

10. Subject has allergy to implant materials (titanium, titanium alloy).

11. Subject has active systemic infection or infection localized to the site of implantation.

12. Subject has primary or metastatic tumors involving the spine.

13. Subject has open wounds or inadequate tissue coverage over the operative site.

14. Subject has a history of significant mental illness or mental incapacity.

15. Subject is pregnant or interested in becoming pregnant in the next 3 years.

16. Subject is currently participating in another investigational study for a similar purpose.

17. Subject belongs to a vulnerable population (e.g., prisoner, severe drug abuser, developmentally disabled) that would compromise ability to provide informed consent or compliance with follow-up requirements.

18. Subject is currently a smoker, and will not cease smoking from the time of clinical trial enrollment up through 3 months post-operatively, nicotine users (cigarettes, patch, gum, etc.) for whom post-operative bone stimulation would be prescribed, or has a recent history of alcohol or other substance abuse within the past 2 years.

19. Subject is receiving workers compensation.

Study Device	Required Components: 

• Stryker AccuLIF TL Interbody Cages and associated instrumentation

• Stryker supplemental fixation and associated instruments

• Autogenous bone and/or allogenic bone graft comprised of cancellous or corticocancellous allograft chips.

Reference Therapy	TLIF with static cage

CONFIDENTIAL

This material is the property of Stryker Spine. Do not disclose or use except as authorized in writing by Stryker.  
Page 11

Ancillary Devices	
The AccuLIF system is indicated for use with autogenous bone and/or allograft (cancellous or corticocancellous allograft chips) and supplemental fixation. Stryker supplementation fixation (Xia or ES2 pedicle screws must be used as part of the study protocol).

Statistical Methodology	
All continuous data will be summarized using continuous descriptive statistics: number of subjects with responses (n), mean, standard deviation, median, minimum, and maximum. Changes from baseline, where appropriate, will be calculated as the follow-up measure minus the baseline measure, where baseline is defined as the last measure prior to the AccuLIF spinal system surgical procedure.
 
All categorical data will be summarized using counts and percentages. Denominators for percentages will be the number of subjects in the respective patient population with nonmissing data.
 
For the primary endpoint of an increase of 3 degrees or more of segmental lordosis, a one-sided analysis (<math>\alpha=0.05</math>) will be used to assess significance. A one-sample t-test will be employed. Although the primary analysis will be at 24 months, similar analyses will be performed at each visit. Both the change from baseline and the results at each visit will be summarized.
 
For all other radiographic parameters, the change from baseline will be analyzed at each visit using two-sided, one-sample t-tests (<math>\alpha=0.05</math>) comparing the change from baseline to 0.
 
Secondary and exploratory endpoints will be analyzed where appropriate. Where changes from baseline can be calculated for numerical data, statistical analyses will be performed. Analyses will follow the two-sided approach taken for the primary analyses. Data that is ordinal in nature, such as the changes in clinical outcomes, may be analyzed using Wilcoxon signed rank tests, comparing baseline measures to follow-up measures. All analyses will be two-sided and evaluated at an alpha level of 0.05.

CONFIDENTIAL

This material is the property of Stryker Spine. Do not disclose or use except as authorized in writing by Stryker.  
Page 12

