## **7.6 12 Month Visit**

During the 12 month visit (365 days after surgery  $\pm$  8 weeks, study days 309 – 421), SF-12, VAS (back and leg), ODI and patient satisfaction will be collected; neurological status (reflex, sensory, motor); subject's current pain medication, work status, and smoking status will be

CONFIDENTIAL

This material is the property of Stryker Spine. Do not disclose or use except as authorized in writing by Stryker.  
Page 21

assessed. AP/Lateral and Flexion/Extension radiographs, and long standing lateral will be taken. CT scan to assess bony fusion, will be taken as well.

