## 9 Statistical Plan

### 9.1 Efficacy Parameters

#### 9.1.1 Primary Objective Parameters

The primary objective parameters of this study are the change in pre-operative to post-operative radiographic outcomes of a cohort treated for degenerative disease at one or two levels implanted with the AccuLIF spinal system at one level via TLIF procedure with supplemental fixation. The primary objective will be evaluated at 12 months post-operatively.

Primary Radiographic parameters are defined as:

- Disc height (anterior, middle, posterior in millimeters)
- Foraminal height (in millimeters)
- Segmental lordosis (at each TLIF level in degrees)
- Regional Lordosis: (inferior endplate T12-S1 in degrees)
- Sagittal balance: (C7-S1 in millimeters)

  

- Success is defined as an increase of 3 degrees or more of segmental lordosis 12 months post operatively.

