#### 9.1.2 Primary Objective Hypothesis

Success is defined as an increase of 3 degrees or more of segmental lordosis post operatively. The primary null hypothesis is as follows:

H0: Subjects implanted with the AccuLIF spinal system will have less than 3 degrees increase in segmental lordosis 12 months post-operatively.

H0: Subjects implanted with the AccuLIF spinal system will have an increase of at least 3 degrees in segmental lordosis 12 months post-operatively.

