#### 9.1.3 Primary Objective Analysis

CONFIDENTIAL

This material is the property of Stryker Spine. Do not disclose or use except as authorized in writing by Stryker.  
Page 25

For the primary endpoint of an increase of 3 degrees or more of segmental lordosis, a one-sided analysis (alpha=0.05) will be used to assess significance. A one-sample t-test will be employed. Although the primary analysis will be at 12 months, similar analyses will be performed at each visit. Both the change from baseline and the results at each visit will be summarized.

For all other radiographic parameters, the change from baseline will be analyzed at each visit using two-sided, one-sample t-tests (alpha=0.05) comparing the change from baseline to 0.

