### 9.4.2 Sample Size Calculation

CONFIDENTIAL

This material is the property of Stryker Spine. Do not disclose or use except as authorized in writing by Stryker.  
Page 27

Sample size calculations are based on the primary analysis of the change from baseline in segmental lordosis at 12 months, utilizing a one-sided, one-sample t-test. Based on previous experience it is assumed that the true change in segmental lordosis after 12 months will be 5 degrees. It is also determined that a change of at least 3 degrees is considered clinically meaningful. With a standard deviation of up to 6 degrees and assuming 90% power, 79 subjects are required to show a difference of at least 3 degrees. Assuming a dropout rate of up 20%, 100 subjects will be enrolled.

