## 16 Publication Plan

It is anticipated that publication of the multi-center study results will be compiled and submitted to a peer-reviewed journal at the time the study cohort reaches 6 weeks, 1 and 2 years of follow-up. Additional publication proposals may be made by investigators at any time and will be considered.

This study will utilize the guidelines for authorship published by the International Committee of Medical Journal Editors (ICMJE). This guidance can be referenced at [www.icmje.org](http://www.icmje.org).

Publications will be facilitated by the Chair and the primary investigator (PI) of the study. Both individuals will be chosen by Stryker.

The PI is solely focused on the multi-center publications and progress towards those publications, including recurring updates to centers, center motivation as well as authorship. If the PI does not produce a draft of a publication within 90 days of receiving the results data, Stryker will delegate the responsibility to other investigators in the study at its discretion.

The Chair reviews all additional publications proposed by participating investigators based upon the study results prior to study completion, on an ongoing basis. This review includes whether or not a proposal will be pursued, as well as imposition of guidelines as to publication completion and criteria.

CONFIDENTIAL

This material is the property of Stryker Spine. Do not disclose or use except as authorized in writing by Stryker.  
Page 38

The following summarizes the possible roles of these parallel positions:

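### The synopsis puts the primary analysis of segmental lordosis at 24 months, Section 9 puts it at 12 months, and nothing says which governs

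*Combined protocol and SAP*

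**What the plan says.** **24 months.** The synopsis, under Statistical Methodology: "Although the primary analysis will be at 24 months, similar analyses will be performed at each visit".

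**12 months.** Four places in Section 9:
- 9.1.1: "The primary objective will be evaluated at 12 months post-operatively". The success definition closing that section names the same visit.
- 9.1.2, null hypothesis: "Subjects implanted with the AccuLIF spinal system will have less than 3 degrees increase in segmental lordosis 12 months post-operatively". The alternative also names 12 months.
- 9.1.3: "Although the primary analysis will be at 12 months, similar analyses will be performed at each visit".
- 9.4.2: "Sample size calculations are based on the primary analysis of the change from baseline in segmental lordosis at 12 months".

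**No visit named.** The synopsis (Hypothesis and Objectives) and Section 2.1 give the success criterion without a date: "Primary success is defined as an increase of 3 degrees or more of segmental lordosis post operatively". The opening sentence of 9.1.2 is undated too.

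**Data and reporting.** AP/lateral films are scheduled at both 12 and 24 months (Evaluation Schedule, 7.6, 7.7). Section 16 expects multi-center results to be "submitted to a peer-reviewed journal at the time the study cohort reaches 6 weeks, 1 and 2 years of follow-up".

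**The concern.** This is a single-arm study with no control cohort. Its formal verdict rests on one one-sided test of the mean gain in segmental lordosis against 3 degrees, and the plan names two different visits for that test.

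The two visits can give different answers. Lordosis gained at surgery may be partly lost later, some patients will drop out between the visits, and sampling variation alone can put the two tests on opposite sides of the threshold. Both results will be produced, and the 12-month result can be in hand before anyone has to decide which page governs. A choice made then could be influenced by the data, and the stated 5% error rate would no longer describe the procedure. Even without any such choice, a reader could not tell from the protocol which result was the pre-specified one.

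**Working it through.** **1. Is the difference explained anywhere?** The Protocol Change History records only the removal of 6-month flexion/extension films and the optional 24-month CT. It does not mention the primary visit. No section ranks the synopsis against the body. Section 9.1.6 mentions a formal statistical analysis plan only as the place where literature sources will be identified. Imaging does not settle the matter: if segmental lordosis is read from the AP/lateral films, it can be measured at both visits.

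**2. The plan's own sample size.** Inputs from 9.4.2 and 9.1.3: true gain 5 degrees, threshold 3 degrees, SD 6 degrees, one-sided alpha 0.05, power 90%.

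Power of the one-sample t-test = P(T > t(0.95, n−1)), where T is noncentral t with n−1 degrees of freedom and noncentrality (5 − 3)/6 × √n.

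| n | Power |
|---|---|
| 78 | 0.8985 |
| 79 | 0.9018 |
| 80 | 0.9051 |

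The smallest n reaching 90% is 79, as stated. Dropout: 79/0.80 = 98.75, so 99, consistent with 100 enrolled. The calculation is correct and is labelled a 12-month calculation. The gain of 5 degrees is tied explicitly to 12 months. The SD and dropout sentences name no visit, but they belong to that calculation. No assumption is stated for 24 months.

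**3. Type I error if the better visit were called primary.** Assume a true mean gain of exactly 3 degrees at both visits and test statistics that are jointly normal with correlation ρ. The documents give no ρ, so a range is shown. Error = 1 − P(Z₁ ≤ 1.645, Z₂ ≤ 1.645).

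| ρ (assumed) | One-sided error |
|---|---|
| 0.9 | 0.068 |
| 0.7 | 0.080 |
| 0.5 | 0.088 |

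**4. How often the two visits would disagree.** Simulated one-sided t-tests, with the same 80 patients at both visits, SD 6, and ρ the patient-level correlation of the two changes (200,000 trials; an independent rerun agreed to within simulation error).

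| True gain, 12 / 24 months | ρ = 0.9 | ρ = 0.7 | ρ = 0.5 |
|---|---|---|---|
| 5 / 5 degrees | 6.1% | 10.3% | 13.0% |
| 5 / 4.5 degrees (24-month value assumed) | 19.3% | 22.6% | 25.7% |

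**5. Power if 24 months were primary.** Same formula as step 2; no correlation enters. The 24-month gains below 5 and the attrition above 20% are assumptions. SD 6 is the plan's upper value, so SD 5 (assumed) is shown beside it.

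| True 24-month gain | Evaluable | Power, SD 6 | Power, SD 5 |
|---|---|---|---|
| 5 | 70 (30% attrition) | 0.868 | 0.952 |
| 5 | 60 (40% attrition) | 0.818 | 0.922 |
| 4.5 | 80 | 0.716 | 0.845 |
| 4 | 80 | 0.434 | 0.551 |

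**6. A separate, minor point.** C7-S1 balance appears to need the long standing lateral film. After surgery that film is scheduled only at 12 months (7.6: "AP/Lateral and Flexion/Extension radiographs, and long standing lateral will be taken"); 7.7 does not list it. Yet 9.1.3 and 9.1.6 call for C7-S1 balance, and the exploratory composite that uses it, to be analyzed at every visit. This has no bearing on the segmental lordosis test.

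**The case against.** The best defence is that this is one uncorrected number in a summary. The dedicated statistical section uses 12 months for the objective, the hypotheses, the analysis and the sample size, and only 12 months has a stated hypothesis and power basis. No passage plans to pick the better result, and Section 16 merely lists publication dates. Section 9.1.3 also already separates one primary visit from similar analyses at the others.

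Much of this stands. Twelve months is the more probable intention, and the error inflation is conditional on someone choosing after seeing data. The 6% to 13% disagreement with equal gains is chance, not bias; it follows from about 90% power at each visit. The 24-month power losses rest on assumed gains, attrition and SD, and they do not arise if 12 months is kept.

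The contradiction itself remains. The synopsis is current protocol text, it states the primary visit outright, and nothing in the document makes Section 9 prevail. The undated success definitions leave both readings open.

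**Conclusion.** The plan is contradictory on the visit that decides its primary test, and this must be corrected. The sample size is not at fault: 79 reproduces, with power 0.902, as a 12-month calculation.

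The consequence depends on how the ambiguity is used. Taking the better visit would raise one-sided error from 5% to about 6.8% to 8.8% (assumed correlations 0.9 to 0.5). Following one page rather than the other would change the verdict in about 6% to 13% of trials if the gain is 5 degrees at both visits, and in about 19% to 26% if the 24-month gain is 4.5 degrees, with 80 patients and SD 6. In that second case 24-month power would be 72%, against 90.5% at 12 months.

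**What to change.** 1. Change the synopsis sentence under Statistical Methodology to 12 months.
2. Add the 12-month visit to the success definition in the synopsis (Hypothesis and Objectives), in Section 2.1, and in the opening sentence of 9.1.2.
3. State in 9.1.3 that segmental lordosis tests at other visits are supportive and cannot establish primary success.
4. If 24 months is the real intention, revise 9.1.1 to 9.1.3 instead, and re-justify 9.4.2 with a gain, SD and dropout rate for that visit.
5. Minor: limit the C7-S1 analysis and the exploratory composite to 12 months, unless the image acquisition protocol (Appendix D, not among the documents reviewed) obtains C7-S1 from another film.

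Keeping 12 months costs wording only, with no new patients, visits or data. Choosing 24 months also means rewriting the sample size justification. Either way, the change should be made before any 12-month result is seen.
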